9.3 FOLLOW UP OF ADVERSE EVENTS

All AEs will be followed until they have abated, or until a stable situation has been reached. Depending on the event, follow up may require additional tests or medical procedures as indicated, and/or referral to the general physician or a medical specialist. AEs and SAEs will be reported if they occur within 1 hour after completion of the EEG-measurement.

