
INTERVENTION

A single EEG measurement with a dry electrode cap (approximately 2 minutes recording duration) will be performed in each patient. In addition, clinical and radiological data will be collected. EEG data will be acquired with a CE approved portable dry electrode EEG device.

MAIN END POINTS

- Primary end point: Based on the EEG data, and using the final diagnosis established by an adjudication committee as the gold standard, one or more novel AI-based EEG algorithms (the AI-STROKE algorithms) will be developed with maximal diagnostic accuracy (i.e. area under the ROC curve; AUC) to identify patients with an LVO stroke of the anterior circulation in a population of patients with suspected AIS.
- Secondary end points:
 - AUC, sensitivity, specificity, positive predictive value (PPV) and negative predictive value (NPV) of the AI-STROKE algorithms based on ambulant EEG for diagnosis of LVO of the anterior circulation in suspected AIS patients in the prehospital setting;
 - AUC, sensitivity, specificity, PPV and NPV of existing EEG algorithms based on ambulant EEG for diagnosis of LVO of the anterior circulation in suspected AIS patients in the prehospital setting;
 - AUC, sensitivity, specificity, PPV and NPV of existing and newly developed EEG algorithms based on ambulant EEG for detection of LVO stroke of the posterior circulation, intracerebral hemorrhage, transient ischemic attack, and stroke mimics;

• Technical and logistical feasibility (e.g. in terms of EEG channel reliability) of paramedics performing ambulant EEG in patients with a suspected AIS in the prehospital setting.

NATURE AND EXTENT OF THE BURDEN AND RISKS ASSOCIATED WITH PARTICIPATION, BENEFIT AND GROUP RELATEDNESS

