A single EEG will be performed in each patient. An EEG-measurement is a safe and non-invasive procedure, regularly performed in standard medical practice. The use of dry electrodes makes it possible to perform the measurement in less than five minutes. The dry electrodes will cause no to minimal discomfort, and only during the measurement. We expect no health risks, as we will use only CE marked products for performing the EEG. The treating physicians and the ambulance paramedics will not interpret the EEG recording, therefore the EEG results will not influence choices regarding diagnosis, treatment or the hospital to which the patient is presented. Deferred informed consent will be asked as soon as logistically feasible, preferably within 72 hours after arrival at the hospital or at discharge (whichever comes first). If informed consent is given, a case report form (CRF) will be filled out containing information on patient characteristics, medical history, medication use, physical and neurological examination performed by the treating physician, results of imaging studies, diagnosis and treatment as well as logistical and technical information, obtained from the patient, the treating physician and the Emergency Medical Service (EMS). There are no follow up visits. For the patient, there is no benefit of participation in the study.

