4.3 EXCLUSION CRITERIA

A potential subject who meets any of the following criteria will be excluded from participation in this study (parts A and B):

- Skin defect or active infection of the scalp in the area of the electrode cap placement;

- (Suspected) COVID-19 infection.

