7.4 SUMMARY OF KNOWN AND POTENTIAL RISKS AND BENEFITS

Since an EEG-measurement is a safe and non-invasive procedure that is regularly performed in standard medical practice, and we only use CE marked products, we expect no health risks and no to minimal discomfort (during the measurement).^{11, 12} The caps will be cleaned and disinfected as recommended in by the manufacturer.

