9.2 AES, SAES AND SUSARS

9.2.1 ADVERSE EVENTS (AES)

Adverse events are defined as any undesirable experience occurring to a subject during the study, whether or not considered related to the investigational product or the intervention. All adverse events reported spontaneously by the subject or observed by the investigator or his/her staff will be recorded.

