9.2.2 SERIOUS ADVERSE EVENTS (SAES)

A serious adverse event is any untoward medical occurrence or effect that:

- Results in death;
- Is life threatening (at the time of the event);
- Requires hospitalisation or prolongation of existing inpatients' hospitalisation;
- Results in persistent or significant disability or incapacity;
- Any other important medical event that did not result in any of the outcomes listed above due to but could have been based upon appropriate judgement by the investigator.

The sponsor will report the SAEs through the web portal *ToetsingOnline* to the accredited METC that approved the protocol, within 7 days of first knowledge for SAEs that result in death or are life threatening followed by a period of maximum of 8 days to complete the initial preliminary report. All other SAEs will be reported within a period of maximum 15 days after the sponsor has first knowledge of the serious adverse events.

Stroke often results in complications such as infections, delirium, constipation, decubitus wounds, swallowing difficulties and falls, as well as in hospitalization and death. Because we expect no health risk related to participation in this study, these events will be reported to the accredited METC that approved the protocol in a yearly line listing until the last patient has completed the study.

Furthermore, the following situations will not be reported as (S)AEs:

- Elective hospitalization for pre-existing conditions that have not been exacerbated by study treatment as judged by the clinical investigator and where admission did not take longer than anticipated;
- Admission and treatment for the index stroke (i.e. the stroke which lead to inclusion of the patient);
- Admission for diagnosis or therapy of a condition that existed before inclusion to this study and has not increased in severity or frequency as judged by the clinical investigator;
- Anticipated day-to-day fluctuations of pre-existing disease(s) or condition(s) present at the start of the study that do not worsen.

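### Section 9.3 opens the AE/SAE reporting window only when the EEG is completed, leaving out the procedure itself and any abandoned EEG, and its 1-hour limit conflicts with section 9.2.2

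*Combined protocol and SAP*

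**What the plan says.** Three parts of chapter 9 bear on which events reach a report.

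- **Section 9.2.1** defines an AE as "any undesirable experience occurring to a subject during the study, whether or not considered related to the investigational product or the intervention", and adds: "All adverse events reported spontaneously by the subject or observed by the investigator or his/her staff will be recorded". It sets no time limit.
- **Section 9.2.2** sets the SAE deadlines: 7 days for fatal or life-threatening events, and otherwise "All other SAEs will be reported within a period of maximum 15 days after the sponsor has first knowledge of the serious adverse events". It sends the usual complications of stroke, including hospital admission and death, to the ethics committee in a yearly listing. Neither rule is tied to the time of the EEG.
- **Section 9.3** sets the only window: "AEs and SAEs will be reported if they occur within 1 hour after completion of the EEG-measurement".

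On timing of effects, the Summary says: "The dry electrodes will cause no to minimal discomfort, and only during the measurement". Section 7.4 places the expected discomfort in the same period ("we expect no health risks and no to minimal discomfort (during the measurement"), though without the word *only*. The Summary also describes the procedure: "A single EEG measurement with a dry electrode cap (approximately 2 minutes recording duration) will be performed in each patient". It puts the whole measurement at under five minutes.

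**The concern.** The reporting window and the expected effect do not overlap. If a site follows section 9.3 to the letter, it reports events from the hour after the EEG. It does not report pain, agitation or a collapse while the cap is being fitted or the recording is running. If the EEG is given up because the patient does not tolerate it or deteriorates, there is no completion to count from, so no window exists for that patient.

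The expected risk is small, but other arrangements rest on that expectation. The EEG is done before consent in patients who gain nothing from it (sections 11.2 and 11.4), there is no safety committee (9.4), and an exemption from subject insurance was granted (11.5). Reported events are one way to check the expectation, so the rule should cover the procedure.

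Sites also face two rules for the same SAE. Section 9.2.2 would have a serious event on day 2 reported or listed, while section 9.3 would leave it out.

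**Working it through.** The plan gives no figure to reproduce, and the point depends on no sample size, event count or error rate. The check sets the rules side by side over the course of one EEG.

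Inputs: recording of about 2 minutes and measurement under five minutes (Summary); 1 hour after completion (9.3); recording rule (9.2.1); SAE deadlines and yearly listing (9.2.2); collected times (8.3).

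| When the event occurs | Recorded under 9.2.1 | SAE reported or listed under 9.2.2 | Reported under 9.3, literal | Reported under 9.3, 1 hour as outer limit |
|---|---|---|---|---|
| Cap placement or recording, EEG later completed | Yes, if observed or volunteered | Yes | No | Yes |
| Completion to 60 minutes later | Yes | Yes | Yes | Yes |
| During or after an EEG that is abandoned | Yes | Yes | No window opens | End of window undefined |
| More than 60 minutes after completion | Yes | Yes | No | No |

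The 9.2.2 column is subject to that section's own list of exempt situations, such as admission for the index stroke.

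1. **First row.** The literal reading leaves out the under-five-minute procedure, the only period in which the Summary expects discomfort. Counting cap placement as part of the measurement is an inference. It fits the gap between about 2 minutes of recording and under five minutes in all, but the documents do not state it.
2. **Third row.** Neither reading settles an abandoned EEG. Section 4.4 shows that failed recordings are foreseen, because it counts them in the assumed dropout.
3. **Fourth row.** Both readings conflict with 9.2.2. Many of the complications it lists would normally arise later than an hour after a single EEG, so a 1-hour limit on all SAEs would largely empty the yearly listing.
4. **Anchors.** Section 8.3 already collects the times of cap placement, start of EEG and stop of EEG. It does not list a time of cap removal.

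**The case against.** The strongest reply is that section 9.3 concerns reporting and section 9.2.1 concerns recording. An event during cap placement is still recorded, so it is not lost. That stands. A reader might infer that the safety data would have no trace of procedure-time events, and the documents do not support this. Some doubt remains about Part A, since 9.2.1 does not say whether a paramedic counts as the investigator's staff, and the description of the paramedic's form in 12.1 names no AE item. The form itself is not in the documents, so no conclusion can be drawn from that.

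Second, 1 hour after completion can fairly be read as an outer limit, with the start left implicit. Section 9.2.2 lists situations that are not reported, and procedure-time events are not among them, which favours this reading. It is plausible, but the text does not state it. It also leaves the abandoned EEG and the conflict with 9.2.2 unresolved.

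Third, a reader might size the problem from the 30% dropout in section 4.4, which is 0.30 x 1192 = 357.6 patients at the maximum enrolment. The documents do not support that use. The 30% combines missing consent with failed recordings, gives no split, and a failed recording may be purely technical. No figure is given for EEGs stopped because of intolerance or deterioration.

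Fourth, a reader might infer that the plan's safety statements would be left without support. Those statements are prior expectations based on CE marking and earlier studies (7.3, 7.4), and safety is not an endpoint in section 8.1. The documents speak of at most minimal discomfort and do not describe the measurement as a source of harm.

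**Conclusion.** The point holds as a defect in a stated rule, and its practical weight is low. Followed as written, section 9.3 leaves the procedure out of AE and SAE reporting, gives no window for an EEG that is not completed, and contradicts section 9.2.2 for later SAEs. The uncovered time is under five minutes per patient who completes the EEG. The number of abandoned EEGs cannot be derived from the documents.

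The first part rests on the literal reading of 9.3 and would fall away if the sponsor confirmed that 1 hour is an outer limit. The second and third parts stand on either reading.

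A reader might go further and infer from the scalp exclusion criterion ("Skin defect or active infection of the scalp in the area of the electrode cap placement") that late scalp lesions also need a reporting rule. That criterion governs eligibility, and the documents contain nothing on when such lesions would appear, so they do not support this extension.

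**What to change.** Reword section 9.3 along these lines: *AEs and SAEs are reported if they start between placement of the EEG cap and 1 hour after the EEG is stopped or abandoned, whether or not the recording was completed.*

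Then reconcile 9.2.1, 9.2.2 and 9.3. State which events are recorded only and which are reported, and whether the SAE deadlines and the yearly listing fall under the 1-hour limit or apply regardless of it.

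The cost is a short amendment and possibly a few more minor AEs to report. No extra visit is needed. The cap-placement and stop times are already collected under 8.3. Only an attempt given up before recording began would lack a stop time, and there the time of abandonment should be noted.

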9.4 SAFETY COMMITTEE

Installation of a safety committee is not deemed necessary, considering that an EEG-measurement is a safe, non-invasive and painless procedure that is used regularly in standard medical practice and only CE marked products are being used.

10. ALGORITHM DEVELOPMENT AND STATISTICAL ANALYSIS

ALGORITHM DEVELOPMENT

The EEG data obtained in the prehospital setting and in the ER will be divided in a training (80%) and validation (20%) set. Only the training set will be used to train novel AI-algorithms for LVO-detection. First, we will create a logistic regression model based on standard EEG-features, e.g. time domain characteristics, power spectral density in different frequency bands, coherence measures, and entropy measures. This model will be the reference to assess the improvement of the other novel AI-based models. We plan to base the final AI-STORKE algorithm on artificial neural networks, but other EEG classification algorithms (e.g. based on support vector machines and random forests) may be explored as well.³⁴ First, we will create convolution neural networks (CNN's) using the extracted EEG-features. Subsequently, we will evaluate whether the EEG-signals contain more information than these features by creating models that analyze the time series directly. To deal with the different timescales of features in EEG-signals and their dynamic behavior, we aim to study recurrent neural networks (RNN's). Examples of such RNN's include Long Short-Term Memory (LSTM)^{35, 36}, Gated Recurrent Unit (GRU) CNN's, and Deep Belief networks (DBN's)³⁷. The first models will be built using a limited set of EEG data since data collection is part of this study. We will deal with the data sparsity using two approaches: (I) Transfer learning, we will train models for other EEG classification tasks (such as classification of stroke vs. healthy subjects or male vs. female), so that features from the time signals are trained. For this, existing fully anonymized EEG data will be used. The trained models will subsequently be used to fine-tune the classification of suspected AIS patients. (II) Reinforcement learning³⁸, and uncertainty-based learning in particular. We will update the models by feeding the data that are collected during the study. During the EEG data collection, the algorithm will be evolving, and the correct classification ratio will be improving as more data are added. The final algorithm will be considered successful if an AUC of >0.80 is reached in the validation set.

STATISTICAL ANALYSIS

EEG data quality will be monitored continuously to avoid an excessive drop-out rate due to malfunctioning EEG hardware. Two interim analyses for the AI algorithms will be performed: the first when 50 and the second when 100 LVO stroke patients are included in the study. Results of these analyses will be obtained by performing k-fold cross-validation on the training data, including data from the ER and the ambulance. The diagnoses (i.e. LVO stroke or no LVO stroke) as predicted by the developed algorithms will be compared to the diagnoses given by the adjudication committee. A receiver operating characteristic (ROC) curve will be plotted for each algorithm and the optimal cut-off value (i.e. highest sensitivity at a specificity \geq 80%) for each algorithm will be determined. For these cut off values, the sensitivity, specificity, negative predictive value and positive predictive value will be reported, including 95% confidence intervals. The steering committee may decide to prematurely stop the recruitment in the study if the results of the interim analysis show that an accurate and stable algorithm can be developed with the data collected up till that point.

Eventually, we will evaluate the performance of the developed classification algorithm(s) and several existing algorithms on the validation data set. A receiver operating characteristic (ROC) curve will be plotted for each algorithm and the optimal cut-off value (i.e. highest sensitivity at a specificity \geq 80%) for each algorithm will be determined. For these cut off values, the sensitivity, specificity, NPV and PPV value will be calculated.

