Large vessel occlusion (LVO) stroke causes around 30% of acute ischemic strokes (AIS) and is associated with severe deficits and poor neurological outcomes.¹⁻⁴ Endovascular thrombectomy (EVT) enormously improves the prognosis of patients with LVO stroke, but its effect is highly time-dependent. Because of its complexity and required resources, EVT can be performed in selected hospitals only. In the Netherlands, approximately half of the EVT-eligible patients are initially admitted to a hospital incapable of performing EVT, and – once it has been ascertained that a patient requires EVT – the patient needs to be transported a second time by ambulance to an EVT-capable hospital.⁵ This workflow leads to an average treatment delay of about 1 hour, which decreases the absolute chance of a good outcome of the patient by 5-15%.⁵⁻ ⁷ To solve this issue, a prehospital stroke triage instrument is needed, which reliably identifies LVO stroke in the ambulance, so that these patients can be brought directly to an EVT-capable hospital. Electroencephalography (EEG) may be suitable for this purpose, since it shows almost instantaneous changes in response to cerebral blood flow reduction.^{8,9} Moreover, significant differences between EEGs of patients with an LVO and those of suspected AIS patients with a smaller or no vessel occlusion have been found.¹⁰ A dry electrode EEG cap enables ambulance paramedics to perform an EEG in the prehospital setting, with significant reduced preparation time compared to conventional wet electrode EEG.^{11, 12} An automatic LVO-detection algorithm will be the key to reliable, simple and fast interpretation of the EEG by paramedics, enabling direct admission of suspected AIS patients to the right hospital.

HYPOTHESIS

An EEG-based algorithm, developed with artificial intelligence (AI), will have sufficiently high diagnostic accuracy to be used by ambulance paramedics for prehospital LVO detection.

OBJECTIVE

The primary objective of this study is to develop one or more novel AI-based algorithms (the AI-STROKE algorithms) with optimal diagnostic accuracy for identification of LVO stroke in patients with a suspected AIS in the prehospital setting, based on ambulant EEG data.

STUDY DESIGN

AI-STROKE is an investigator-initiated, multicenter, diagnostic test accuracy study.

STUDY POPULATION

Part A: Adult patients with a (suspected) AIS, in the prehospital setting.

Part B: Adult patients with a (suspected) AIS, in the in-hospital setting.

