2. OBJECTIVES

The primary objective of this study is to develop one or more novel AI-based algorithms (the AI-STROKE algorithms) with optimal diagnostic accuracy for identification of LVO stroke in patients with a suspected AIS in the prehospital setting, based on ambulant EEG data.

The secondary objectives are:

- Assessing the diagnostic accuracy of existing EEG algorithms for identification of LVO stroke in patients with a suspected AIS in the prehospital setting;
- Improving the applicability and reliability of the dry electrode EEG cap for use in the prehospital setting;
- Assessing the logistical and technical feasibility of ambulance paramedics performing ambulant EEGs, using an improved dry electrode EEG cap, in the prehospital setting in patients with a suspected AIS.

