8. METHODS

8.1 STUDY PARAMETERS/END POINTS

8.1.1 MAIN STUDY PARAMETER/END POINT

Based on the EEG data one or more novel AI-based EEG algorithms (the AI-STROKE algorithms) will be developed with optimal diagnostic accuracy for identification of LVO stroke in patients with a suspected AIS in the prehospital setting. For the purpose of the study, an LVO is defined as an occlusion of:

- Intracranial part of the internal carotid artery (ICA)
- First segment or proximal part of the second segment of the middle cerebral artery (M1 and proximal M2, respectively)
- First segment of the anterior cerebral artery (A1)

The final diagnosis of all patients will be established by an adjudication committee, which will consist of a vascular neurologist and neuroradiologist, and will be based on available clinical and imaging data.

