8.1.2 SECONDARY STUDY PARAMETERS/END POINTS

Secondary end points of this study are:

- AUC, sensitivity, specificity, positive predictive value (PPV) and negative predictive value (NPV) of the AI-STROKE algorithms based on ambulant EEG for diagnosis of LVO of the anterior circulation in suspected AIS patients in the prehospital setting;
- AUC, sensitivity, specificity, PPV and NPV of existing EEG algorithms based on ambulant EEG for diagnosis of LVO of the anterior circulation in suspected AIS patients in the prehospital setting;
- AUC, sensitivity, specificity, PPV and NPV of existing and newly developed EEG algorithms based on ambulant EEG for detection of LVO stroke of the posterior circulation, intracerebral hemorrhage, transient ischemic attack, and stroke mimics;
- Technical and logistical feasibility (e.g. in terms of EEG channel reliability) of paramedics performing ambulant EEG in patients with a suspected AIS in the prehospital setting.

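### Chapter 10 does not restrict the validation set by entry route, so patients enrolled with an already confirmed LVO enter accuracy estimates meant for suspected-AIS patients

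*Combined protocol and SAP*

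**What the plan says.** **Population named.** Section 2 sets the objective as "identification of LVO stroke in patients with a suspected AIS in the prehospital setting, based on ambulant EEG data". Section 8.1.1 has the algorithms developed with "optimal diagnostic accuracy for identification of LVO stroke in patients with a suspected AIS in the prehospital setting". The primary end point in the Summary is "to identify patients with an LVO stroke of the anterior circulation in a population of patients with suspected AIS". The first two secondary end points in section 8.1.2 ask for AUC, sensitivity, specificity, PPV and NPV "for diagnosis of LVO of the anterior circulation in suspected AIS patients in the prehospital setting".

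**Population enrolled.** Sections 3, 4.1 and 4.2 give two alternative ways in, for both parts: suspicion of AIS by the paramedic, or an LVO that is already known. Section 3 describes the second group as radiologically confirmed LVOs being taken to an EVT centre (Part A) or to the AMC for EVT (Part B).

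**Population analysed.** Chapter 10 says: "The EEG data obtained in the prehospital setting and in the ER will be divided in a training (80%) and validation (20%) set". It then says: "The final algorithm will be considered successful if an AUC of >0.80 is reached in the validation set". For the final evaluation: "Eventually, we will evaluate the performance of the developed classification algorithm(s) and several existing algorithms on the validation data set", with sensitivity, specificity, NPV and PPV taken at the cut-off with the highest sensitivity at a specificity of at least 80%. The two interim analyses use cross-validation on the training data from both settings. None of these steps separates patients by entry route.

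**The concern.** Known LVOs are cases selected on the reference standard. There is no matching route for patients already known not to have an LVO. They also do not face the triage question of chapter 1, which is which suspected patients should go directly to an EVT-capable hospital.

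If they sit in the validation set, three things follow. The proportion of LVO in the set exceeds that among suspected-AIS patients, which moves PPV and NPV. The reported sensitivity averages over known LVOs and LVOs found among suspected patients. The AUC does the same, so a pass or fail at 0.80 is not a result for the population in the end points. Specificity, and the requirement that it be at least 80%, rest on non-LVO patients and are largely unaffected.

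**Working it through.** **1. The plan's own sample size (section 4.4).** Inputs: 40 to 100 LVO events, 12% LVO among suspected AIS, 30% dropout.
- Upper end: 100 / 0.12 = 833.3, so 834; 834 / 0.70 = 1191.4, so 1192. This matches.
- Lower end: 40 / 0.12 = 333.3, so 334; 334 / 0.70 = 477.1, so 478, against 484 stated. The gap of 6 is about 1% and does not matter here.

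The calculation counts suspected-AIS patients only. At the maximum, 1192 × 0.70 = 834 are evaluable and 0.20 × 834 = 167 fall in the validation set. That set holds about 0.12 × 167 = 20 LVOs, or 0.07 × 167 = 12 at the 7% given in chapter 1.

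**2. PPV and NPV with k known LVOs among the 834.** The documents do not give k, so a range is shown. Sensitivity (Se) 0.70 and specificity (Sp) 0.80 are assumed.
- Prevalence P = (k + (834 − k) × p) / 834, with p = 0.12 or 0.07.
- PPV = P × Se / (P × Se + (1 − P) × (1 − Sp)).
- NPV = (1 − P) × Sp / ((1 − P) × Sp + P × (1 − Se)).
- Known share of LVO cases s = k / (k + p × (834 − k)).

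Example, k = 50 and p = 0.12: P = (50 + 94.1) / 834 = 0.173; PPV = 0.121 / (0.121 + 0.165) = 0.42.

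| k | PPV, p = 12% | NPV, p = 12% | s, p = 12% | PPV, p = 7% | NPV, p = 7% |
|---|---|---|---|---|---|
| 0 | 32% | 95.1% | 0% | 21% | 97.3% |
| 10 | 34% | 94.7% | 9% | 24% | 96.8% |
| 25 | 38% | 94.0% | 20% | 28% | 96.1% |
| 50 | 42% | 92.7% | 35% | 33% | 94.9% |
| 100 | 50% | 90.2% | 53% | 44% | 92.3% |

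**3. AUC.** Against the same non-LVO patients, the AUC of the mixed set is (1 − s) × (AUC for LVOs among suspected AIS) + s × (AUC for known LVOs). Prevalence alone does not enter. The two component AUCs are not in the documents, so neither the size nor the direction of a shift can be derived.

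**4. Pooling ambulance and ER.** This was checked with a binormal model: within-setting AUC 0.75, 30% ER share, score shift of 0.5 to 1 SD either way, all assumed. With 12% LVO in both settings the pooled AUC is 0.730 to 0.745. With 7% in the ambulance and 12% in the ER, also assumed, it runs from 0.698 to 0.759. It can go either way, so no size is claimed.

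**5. Precision after restriction.** Hanley-McNeil at A = 0.80: SE² = [A(1 − A) + (m − 1)(A/(2 − A) − A²) + (n − 1)(2A²/(1 + A) − A²)] / (mn), with m LVOs and n non-LVOs. For 20 and 147: (0.16 + 19 × 0.0267 + 146 × 0.0711) / 2940 = 0.00376, so SE = 0.061.

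| Validation set | LVO / non-LVO | SE | Normal 95% limits |
|---|---|---|---|
| All suspected AIS, 12% | 20 / 147 | 0.061 | 0.68 to 0.92 |
| Half of these in Part A | 10 / 73 | 0.087 | 0.63 to 0.97 |
| All suspected AIS, 7% | 12 / 155 | 0.078 | 0.65 to 0.95 |
| Half of these in Part A | 6 / 78 | 0.111 | 0.58 to above 1 |

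**The case against.** **Chapter 10 is silent rather than contrary.** Section 8.1.2 already names the population of the first two secondary end points, and section 3 heads validation separately for the prehospital setting and the ER. An analyst could honour both. This stands to the extent that nothing in the documents says the end-point population is overridden, and a reader who infers a deliberate choice to score known LVOs goes too far. But chapter 10's split covers all ambulance and ER data, and section 3 assigns Part A data, known LVOs included, to both development and validation. Restricting to ambulance recordings would not remove the Part A transfers.

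**Suspected may be shorthand.** The Summary describes Part A as "Adult patients with a (suspected) AIS, in the prehospital setting", with the qualifier in brackets. That wording covers who is enrolled. Sections 3, 4.1 and 4.2 list known LVO as a separate alternative, and the end points do not mention it.

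**The size is assumed.** This stands. The documents give no number of known LVOs, no expected sensitivity and no split between parts. Section 3 enrols each patient once, which rules out a second recording in Part B. The bottom row of the table implies 100 + 0.12 × 734 = 188 LVOs, well past the second interim analysis at 100 LVOs, where recruitment may stop. The documents' own two prevalences, 7% and 12%, move PPV from 21% to 32%, about as much as 50 known LVOs do.

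**PPV and NPV can be recalculated at another prevalence.** Only partly. The sensitivity used in that recalculation would still mix the two kinds of case.

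**Conclusion.** The mismatch holds on the text and does not depend on any assumed figure: the end points name one population, and chapter 10, followed as written, evaluates a wider one. It should be corrected before the validation data are evaluated.

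The size depends on how many known LVOs are enrolled. Under the assumptions in the working (sensitivity 0.70, specificity 0.80, 834 evaluable, 12% base prevalence), PPV moves from 32% to between 34% and 50%, and NPV from 95.1% to between 94.7% and 90.2%, for 10 to 100 known LVOs. Ten make little difference.

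Two stronger readings are not supported. A reader might infer that known LVOs inflate the AUC and make 0.80 easier to reach. That would need them to be easier to separate than LVOs among suspected patients; the documents do not say so, and the reverse would lower the AUC. A reader might also infer that pooling ambulance and ER recordings is in itself harmful, or in itself negligible. The answer depends on prevalences and score shifts that the documents do not give. Apart from known LVOs, Part B patients also enter on a paramedic's suspicion.

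**What to change.** In chapter 10:

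1. Record entry route (suspected AIS or known LVO). Assign every patient whose LVO was confirmed before the EEG to training only. Split only suspected-AIS patients 80/20, stratified by part.
2. Apply the AUC criterion and the LVO accuracy end points (the primary and the first two secondary) to suspected-AIS validation patients. Report AUC by setting. Compute the first two secondary end points on Part A suspected-AIS validation patients, and base any prehospital conclusion on that estimate with its 95% confidence interval.
3. At the interim analyses, allow known LVOs to help fit the models in each fold, but compute cross-validated AUC, sensitivity, PPV and NPV on suspected-AIS patients only. These results inform early stopping, and step 1 raises the share of known LVOs in the training data.

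This needs text and one recorded item, which can largely be derived from the transfer and imaging times listed in section 8.3. No patients or procedures are added, and known LVOs are kept for training.

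The cost is precision, which should be stated with the results. The intervals in the working are the best case at maximum enrolment: about 20 validation LVOs at 12% prevalence, and about 6 if prevalence is 7% and half the patients are in Part A. In that last case the prehospital estimate could be uninformative.
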